Among pregnant women, a cohort design will be used to compare the incidence of pregnancy outcomes (spontaneous abortion, stillbirth, and preterm birth) among those who were exposed to Pfizer-BioNTech bivalent COVID-19 Vaccine during pregnancy compared with that among those who were unexposed to any COVID-19 vaccine during pregnancy (Figure 2). Similarly, a cohort design will be used to compare the prevalence of birth outcomes (major congenital malformations and small size for gestational age) in infants who were born to pregnant women who were exposed to Pfizer-BioNTech bivalent COVID-19 Vaccine during pregnancy compared with that in infants born to pregnant women who were unexposed to any COVID-19 vaccine during pregnancy (Figure 3). Exposed and unexposed pregnant women will be matched on estimated pregnancy start (date of last menstrual period [LMP]), gestational age at cohort entry (for pregnancy outcomes only), maternal age, and US state (if feasible, or broader geographic region if not feasible). Inverse probability of treatment weighting will be used to account for additional confounders.

[figure not shown]
090177e19f732934\Approved\Approved On: 14-Dec-2023 13:35 (GMT)

Figure 2. Cohort design to assess pregnancy outcomes

COVID-19 = coronavirus disease 2019; LMP = date of last menstrual period.

Figure 3. Cohort design to assess birth outcomes

COVID-19 = coronavirus disease 2019; LMP = date of last menstrual period.

A strength of a cohort design with concurrent unexposed comparators is that, unlike the SCRI design, it can be used to study safety events for which the risk varies substantially over time (such as spontaneous abortion) and/or for which the timing of onset is unknown (such as major congenital malformations and small size for gestational age). The use of a contemporaneous comparator rather than a historical comparator avoids bias due to temporal trends in coding for outcomes. Limitations of the cohort approach include the potential for bias due to misclassification of exposed individuals as “unexposed” comparators and bias due to confounding when comparing exposed with unexposed pregnant women.

Confounding will be handled by matching and inverse probability of treatment weighting.

To assess the feasibility for planned analyses, a monitoring analysis will be conducted to describe vaccine utilization among the overall population, among immunocompromised

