9.2.1.2. Population to assess pregnancy and birth outcomes

Pregnant women aged between 12-55 years will be eligible for inclusion in the final analysis of pregnancy and birth outcomes if they had a recorded pregnancy outcome (eg, live birth, stillbirth, spontaneous abortion, ectopic pregnancy, pregnancy termination) during the study period. As pregnancy status is not directly recorded in Sentinel data sources, an algorithm (to be defined in the SAP) that incorporates diagnosis and/or procedure codes will identify pregnancy episodes and pregnancy outcomes as well as the estimated start (estimated LMP) and end of pregnancy. Livebirth pregnancies identified in maternal data will be linked with infant data to identify birth outcomes during the first year of life (Sentinel, 2019). Additional cohort eligibility criteria are described below for each of the pregnancy and birth outcomes.

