Comorbidities (in the 12 months before the index date); separate variables for the following conditions: 
 • History of anaphylaxis • History of vaccine-related allergies • Diabetes (type 1 and type 2) • Hypertension • Cardiovascular disease • Cerebrovascular diseases • Chronic respiratory disease • Chronic kidney disease • Chronic liver disease • Cancer • Epilepsy • Infections • Connective tissue disorders • Thyroid disorders • Mood disorders • Asthma • Obesity (capture anticipated to be incomplete in the data sources) 		X		X
Healthcare utilization in the 12 months before or on the index date		X		X
Alcohol abuse and smoking in the 12 months before or on the index date (capture anticipated to be incomplete)		X		X
Reproductive history (in all data available before the index date; if feasible in the data sources): 
 • Spontaneous abortions in previous pregnancies • Pregnancy terminations in previous pregnancies 		X		X
Pregnancy complications during the current pregnancy ^d : 
 • Multiple pregnancy • Gestational diabetes • Preeclampsia/eclampsia • TORCH infections 		X		X
Teratogenic medications (from 28 days before pregnancy start until end of pregnancy ^d)		X		X

090177e19f732934\Approved\Approved On: 14-Dec-2023 13:35 (GMT)

Table 7. Covariates used for descriptive analysis, matching or propensity score estimation

Variable	General safety events	Pregnancy and birth outcomes		
	Descriptive	Descriptive	Matching	Propensity scores

COVID-19 = coronavirus disease 2019; LMP = date of last menstrual period; TORCH = toxoplasmosis, other (syphilis, varicella-zoster, parvovirus B19), rubella, cytomegalovirus, and herpes infections.

a. To be assessed on the index date for general safety events and on LMP for pregnancy and birth outcomes.

b. To be assessed on the index date for analysis of general safety events and from 28 days before LMP until end of pregnancy for pregnancy and birth outcomes. Only information up to and including the index date will be included in propensity scores.

c. Applies only to pregnancy outcomes analysis.

d. Except for multiple pregnancy, only information up to and including the index date will be included in propensity scores.

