9.7.2. Analysis of pregnancy and birth outcomes

Among pregnant women, the distribution of demographics, comorbidities, and other potential confounders will be reported and compared between the matched exposed and unexposed cohorts. Covariate balance in the matched and weighted cohorts will be assessed using standardized differences or other suitable methods.

Vaccinated pregnant women will be matched to pregnant unexposed comparators in a ratio of exposed:unexposed of at least 1:1 on maternal age, US state (if feasible, or broader geographic region if not feasible), and pregnancy start (to address confounding by calendar time). Confounding by other variables will be addressed using inverse probability of treatment weighting, based on propensity scores estimated in the matched population.

In each data RP, measures of incidence or prevalence of pregnancy and birth outcomes and associated 95% CIs will be estimated within the matched exposed and unexposed cohorts.

Cox models or Poisson regression will be used to calculate adjusted HRs or incidence rate ratios and 95% CIs for spontaneous abortion, stillbirth, and preterm birth. For major congenital malformations and small size for gestational age, logistic regression will be used to estimate PORs and 95% CIs.

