9.7.3.3. Confounding

Comparisons between vaccinated and unvaccinated pregnant women may be confounded, as unvaccinated women may differ substantially with respect to health-seeking behaviors and other risk factors for pregnancy and birth outcomes. For pregnancy and birth outcomes, a sensitivity analysis will be performed among pregnant women with a recorded history of monovalent COVID-19 vaccination before cohort entry, which may serve as a proxy for these health-seeking behaviors. This sensitivity analysis will also address potential misclassification of unexposed status, as women with a recorded history of monovalent COVID-19 vaccination may have more complete data on bivalent COVID-19 vaccination.

Confounding by time-invariant characteristics is not a concern in the SCRI design because it is self-controlled.

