A study design–related limitation is that the SCRI design (which is planned to assess general safety events) is more sensitive than a cohort design to misspecification of risk and control intervals. However, the SCRI design presents a strong alternative to a cohort design because it inherently adjusts for time-invariant confounders, including prior history of COVID-19 vaccination, which may be difficult to assess in claims data. While the SCRI design can generally be subject to time-varying confounding, the buffer and control intervals for each general safety event will be defined (in the SAP) to minimize this potential source of bias by minimizing each person's total duration of observation. Sensitivity analyses with alternative risk intervals will be considered for outcomes for which signals have been observed in other safety surveillance systems or studies and risk intervals that are not well characterized.

A limitation of the cohort design, which will be used to assess pregnancy and birth outcomes, is the potential for residual or unmeasured confounding, because it is unlikely that the data RPs will have information on all potential confounders. However, the cohort design presents a viable alternative to the SCRI design; unlike the SCRI design, it is suitable to assess safety events for which the risk varies substantially over time (such as spontaneous abortion) and/or the timing of onset is unknown (such as major congenital malformations and small size for gestational age). To address the potential for unmeasured confounding, sensitivity analysis will be performed among pregnant women with a history of monovalent COVID-19 vaccine

PFIZER CONFIDENTIAL

receipt, which may serve as a proxy for health-seeking behaviors and risk factors for pregnancy outcomes.

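### The propensity score's reproductive history covers only prior spontaneous abortions and terminations, which may leave avoidable residual confounding for stillbirth, preterm birth and small size for gestational age

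*Protocol*

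**What the plan says.** Protocol Section 9.7.2 makes weighting the main control for confounding beyond the matching factors: "Confounding by other variables will be addressed using inverse probability of treatment weighting, based on propensity scores estimated in the matched population". Table 7 in Section 9.3.3 names the covariates that enter those scores. Its obstetric-history row reads "Reproductive history (in all data available before the index date; if feasible in the data sources") and has two entries, "Spontaneous abortions in previous pregnancies" and "Pregnancy terminations in previous pregnancies". The row is marked for description and for the propensity score.

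The matching set carries no obstetric history. Section 9.1 says "Exposed and unexposed pregnant women will be matched on estimated pregnancy start", and adds gestational age at cohort entry (pregnancy outcomes only), maternal age, and state or region. No other Table 7 row covers prior stillbirth, prior preterm birth or a prior small-for-gestational-age infant. The abstract mentions reproductive history without itemising it.

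Section 9.2.1.2 plans an algorithm that "incorporates diagnosis and/or procedure codes will identify pregnancy episodes and pregnancy outcomes as well as the estimated start (estimated LMP) and end of pregnancy", and links live births to infant data.

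**The concern.** For these endpoints, the outcome of an earlier pregnancy is the nearest thing to a baseline value. Table 7 supplies it for spontaneous abortion but not for stillbirth, preterm birth or small size for gestational age, and gives no reason for the difference.

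The protocol itself expects the compared groups to be unlike, "as unvaccinated women may differ substantially with respect to health-seeking behaviors and other risk factors for pregnancy and birth outcomes" (Section 9.7.3.3). If a previous adverse outcome predicts recurrence and also differs between vaccinated and unvaccinated women after matching and weighting, leaving it out biases the estimate. A bias below 1 would tend to hide harm; a bias above 1 would tend to create a false signal. Preterm birth is most exposed to this, because its planned precision is high enough for a small bias to affect the test.

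The omission also looks avoidable. The planned algorithm identifies pregnancy outcomes with start and end dates. Applied to the look-back the row already specifies, it would yield prior stillbirth and prior preterm birth. A prior small-for-gestational-age infant could come from the mother-infant linkage and the codes in Table 6.

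**Working it through.** **Inputs from the protocol (Section 9.5.2).** Two-sided alpha 0.05, 1:1 groups. Stillbirth 0.5%, HR 1.2, 100,000 per group, stated power 0.851. Preterm birth 10%, 20,000 per group, stated power 1.000 at HR 1.2.

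**Inputs that are assumptions.** The prevalence of the prior outcome in exposed (pe) and unexposed (pu) women, and its recurrence ratio (R). The protocol gives none of these, so ranges are shown.

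**Reproducing the plan's figures.** Power = Phi(sqrt(events/4) × ln HR − 1.96), with events = n × (p0 + p1) and p1 = 1 − (1 − p0)^HR.
- Stillbirth: p1 = 1 − 0.995^1.2 = 0.0060; events = 100,000 × (0.0050 + 0.0060) ≈ 1,100; sqrt(1,100/4) = 16.58; 16.58 × 0.1823 − 1.96 = 1.063; power 0.856 against the stated 0.851.
- Preterm birth: power above 0.9999 against the stated 1.000.

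Table 9 is reproduced. This point disputes none of its numbers.

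**Bias from an omitted history.** Factor = (1 + pe(R − 1)) / (1 + pu(R − 1)). If pe = pu, the factor is 1.00 for any R.

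**Preterm birth with no true effect.** Events ≈ 2 × 20,000 × 0.10 = 4,000; SE(log HR) = sqrt(4/4,000) = 0.0316. With z = ln(factor)/SE, the rejection probability is Phi(−1.96 − z) + Phi(−1.96 + z).

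| pe, pu, R (assumed) | Factor | z | Rejection (nominal 5%) |
|---|---|---|---|
| 2.0%, 2.8%, 3 | 1.040/1.056 = 0.985 | −0.48 | 7.7% |
| 5%, 6%, 2 | 1.05/1.06 = 0.991 | −0.30 | 6.0% |
| 5%, 7%, 3 | 1.10/1.14 = 0.965 | −1.13 | 20.4% |

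Reversing the first imbalance (2.8% exposed, 2.0% unexposed) gives 1.015 and the same 7.7%, so the direction is open.

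**Plausibility of the recorded prevalences.** At a 10% preterm rate and one earlier delivery per woman, recorded prevalences of 2.0% and 2.8% need about 20% and 28% of women to have a previous delivery inside the look-back. Prevalences of 5% and 7% need 50% and 70%. Section 9.9 reports that 47% of individuals in the distributed database have at least 2 years of enrollment and 36% at least 2.5 years. The first row of the table is therefore easier to reconcile with the data than the last.

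**Stillbirth with true HR 1.2, 100,000 per group.** Prior-stillbirth prevalence is assumed near the protocol's 0.5% rate: 0.5% exposed, 0.7% unexposed.
- R = 3: factor 1.010/1.014 = 0.996; apparent HR 1.195; 16.56 × 0.1784 − 1.96 = 0.994; power 0.840.
- R = 5: factor 1.020/1.028 = 0.992; apparent HR 1.191; 16.55 × 0.1745 − 1.96 = 0.927; power 0.823.

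No magnitude was computed for small size for gestational age.

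**The case against.** The strongest objection is that the documents do not establish confounding. It requires the history to differ by vaccination status after matching on pregnancy start, maternal age and region and after weighting, and no section says that it does. This stands, and it limits the point to possible residual confounding. Diabetes, hypertension, obesity, smoking, healthcare utilization and prior losses are already in the score and would absorb part of any bias, so the factors above are upper bounds for their inputs.

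A reader might carry the preterm-history prevalences over to stillbirth and infer that its power falls far below 85%. The documents do not support that: the protocol puts stillbirth at 0.5%, and prior-stillbirth prevalences near that level move power by only 2 to 3 points.

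The protocol also acknowledges the general problem. Section 9.9 says the limitation "is the potential for residual or unmeasured confounding, because it is unlikely that the data RPs will have information on all potential confounders", and Section 9.7.3.3 commits to an analysis restricted to women with recorded monovalent vaccination. Neither fully answers the point. The restriction is a proxy for health-seeking behavior and does not measure obstetric history, and the caveat concerns information the data partners lack, whereas this information is partly available.

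Short enrollment limits what can be captured. That is true, but it applies equally to the two items already listed.

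Finally, Section 9.7 allows the SAP, which is not at hand, to modify the plan and perhaps extend the list. The protocol nevertheless states the list and marks it for the score, so the list as stated is what can be reviewed. Major congenital malformations likewise have no own-outcome history in Table 7; that outcome was not examined here.

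**Conclusion.** The point holds as an inexpensive improvement to the covariate list; the protocol contains no numerical error here. As written, prior stillbirth, prior preterm birth and a prior small-for-gestational-age infant are not directly adjusted, which may leave avoidable residual confounding for those three outcomes.

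Under the assumed inputs, the effect on preterm birth runs from slight (6% to 8% false rejection) to material (about 20%), with the milder end easier to square with the enrollment spans. For stillbirth the effect is small: about 82-84% power instead of 85%. All of this rests on assumed prevalences and recurrence ratios. The direction is unknown, and the bias is zero if the histories are equally common in both groups. It would go too far to say that the omission does confound these estimates.

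**What to change.** In the reproductive-history row of Table 7, add:
- stillbirth in previous pregnancies;
- preterm birth in previous pregnancies;
- a small-for-gestational-age infant in a previous pregnancy, where a prior linked infant exists;
- an indicator for any recorded prior pregnancy, so that no prior event is distinguished from no prior pregnancy observed.

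Mark all four for description and for the propensity score, under the row's existing look-back and feasibility condition.

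The cost is four binary covariates from the pregnancy algorithm and infant linkage already planned. No design feature, sample size or stated power figure changes. The drawbacks are sparse cells at smaller data partners and, because enrollment histories are short, only partial correction; the report should say so.

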9.4. Data sources

The study will use data from data RPs that contribute claims and electronic health records to the Sentinel System. The data sources planned for inclusion in this the study are CVS Health (Aetna Research Database), Carelon Research (formerly HealthCore), HealthPartners, Humana, and Optum Research Database. The participation of these RPs in the general safety and/or pregnancy and birth outcome analyses will be confirmed before finalizing the SAP; additional data sources may be added.

Inclusion of data sources for specific analyses will be based on the following:

- Anticipated number of Pfizer-BioNTech bivalent COVID-19 vaccinees
- Coverage of special populations of interest (eg, pregnant women, pediatric population, individuals aged ≥ 65 years)
- Ability to identify pregnant women and link them to their infants
- Lag in claims and/or structured electronic health records data
- Availability, quality, and timing (frequency and lag) of data from immunization registries

The FDA Sentinel System is an active surveillance system that uses routine querying and analytical tools to evaluate electronic healthcare data from a distributed data network for monitoring the safety of regulated medical products in the US, established under the Sentinel Initiative (Behrman et al., 2011; Platt et al., 2018). Sentinel data RPs typically update their curated Sentinel database on a routine (tri-annually or annually) basis. This study will focus on the research-eligible populations from each of the RPs participating in the study and will use the most recent data available within each participating partner’s Sentinel Distributed Database at the time of analysis.

090177e19f732934\Approved\Approved On: 14-Dec-2023 13:35 (GMT)

All data RPs that participate in Sentinel capture longitudinal medical care information on outpatient medication dispensings, vaccine administrations, and inpatient and outpatient diagnoses and procedures. The data RPs also capture member demographic and health plan enrollment information. Each data RP can request access to full-text medical records for outcome validation for a subset of participants in the Sentinel Distributed Database. Data RPs use the Sentinel Common Data Model (SCDM) (Curtis et al., 2012; Sentinel, 2022) to standardize demographic and clinical data elements. Publicly available routine analytical tools (ie, reusable, modular SAS [SAS Institute Inc.; Cary, North Carolina] programs) designed to be executed against the SCDM permit standardized queries across data from different partners, including descriptive analyses and complex methodologies (eg, comparative analyses).

9.4.1. CVS Health, Aetna

Aetna, a CVS Health company, is one of the US's leading healthcare benefits companies, currently serving 39 million people. Aetna became part of the Sentinel System in 2008. Aetna's SCDM captures longitudinal information on dispensed prescriptions, inpatient and outpatient diagnoses, inpatient and outpatient treatments and procedures, and outpatient laboratory results. The healthcare experience for over 34 million individuals is available for research, covering all ages, with a median (range) age of 45 (0-119) years (based on individuals' most recent available data).

9.4.2. Carelon Research (formerly HealthCore, Inc.)

Carelon Research (formerly HealthCore, Inc.) became a participant in the Sentinel System in 2008 and contributes both by submitting data to the Sentinel database and as a collaborator. As of June 2022, there were 80 million unique individuals with medical coverage and approximately 62 million with medical and pharmacy coverage available for research, covering all ages, with a median age of 40 years and an interquartile range of 26-57 years.

9.4.3. HealthPartners

HealthPartners is the largest consumer-governed nonprofit healthcare organization in the US, providing care, insurance coverage, research, and education to its members and patients. HealthPartners operates primarily in the Midwest and serves more than 1.8 million medical and dental health plan members and more than 1.2 million patients, covering all ages, with a median age of 39 years and a range of 0-110 years. HealthPartners and its associated research team, HealthPartners Institute, became a member of the Sentinel System in 2008.

9.4.4. Humana

Humana Healthcare Research is a health economics and outcomes research subsidiary of Humana, which focuses on treatment effectiveness, drug safety, adherence, medical and pharmacy benefit design, disease management programs, and other healthcare services based on the Humana health plan member population. Humana Healthcare Research is an active collaborator and data RP in the Sentinel System. The Humana research-eligible database represents geographic coverage for the entire US population (Puerto Rico excluded) and as of 31 Dec 2022 has 31 million unique individuals, covering all ages, with a median age of 67 years and a mean continuous enrollment of 55.3 months.

9.4.5. Optum Research Database

The Optum Research Database is a proprietary research database that includes data drawn from a large US health plan affiliated with Optum. It contains eligibility data and medical and pharmacy claims for health plan members who are geographically diverse across the US. The Optum Research Database comprises approximately 3% to 4% of the US population, covering all ages, with a median age of 36 years and an interquartile range of 21-51 years. Optum has curated and quality-checked data formatted to the SCDM available for use and is a longtime participant in the Sentinel System.

